## **6. Adverse events/reactions data collection and report**

### **6.1 Definitions**

#### **6.1.1 Definition of adverse event (AE).**

Adverse event (AE) is any untoward change in state of health of patient or clinical investigation/trial subject administered a pharmaceutical/studied product and which does not necessarily have to have a causal relationship with this treatment. AE can be any unfavorable symptom (for example, nausea, chest pain), sign (for example, tachycardia, enlarged liver) or abnormal examination result (for example, abnormal laboratory finding, change in ECG), the time

of occurrence of which does not exclude causal relationship with the use of a pharmaceutical product, whether or not related to the use of a pharmaceutical product.

The term AE is used to indicate both serious and non serious adverse events.

The data on special situation should also be collected and reported: the use of a pharmaceutical product during pregnancy or lactation (whether the pregnancy outcome is known or not), lack of treatment efficacy, overdose, abuse, misuse, off-label use, suicidal attempt or completed suicide, suspected drug interaction and suspected infectious agent transmission.

### **6.1.2 Definition of serious adverse event (SAE).**

Serious adverse event is AE, that occurs at any stage of the trial (i.e. introductory stage, observation stage) and meets one or more of the following criteria:

- Results in death;
- Is life-threatening (in this context, a reaction can be defined as life-threatening if it places the patient at immediate risk of death from the reaction as it occurred; it does not include a reaction that, had it occurred in a more severe form, might have caused death).
- Requires inpatient hospitalization or prolongation of existing hospitalization;
- Results in persistent or significant disability/incapacity;
- Is a congenital anomaly/birth defect;
- Is any other clinically significant medical event, that can be menacing to the patient or requires medical treatment to prevent the previously-mentioned conditions. The compliance of AE with the criteria of seriousness can be determined using medical and scientific consideration.

Any suspected unintentional transmission of an infectious agent is also defined as SAE and may be subject to express reporting in some countries. An infectious agent is any microorganism, virus or infectious particle (for example, a prion protein that is a carrier of transmissible spongiform encephalopathy), regardless of pathogenicity.

### **6.1.3 Definition of adverse reaction (AR)**

Adverse reaction (AR) is AE, related to the use of pharmaceutical/studied product and implying at least probable interrelation with the use of suspected pharmaceutical/studied product.

Adverse reaction may occur by use of the pharmaceutical product in accordance with instructions for medical use or not in accordance with it, and also by impact, associated with the occupation.

## **6.2 Adverse events data collection**

In view of the non-interventional nature of this study, active collection of safety data will not be performed. It applies to collection of both primary safety data – (directly from patients) and secondary data (analysis of patient's medical records, available at the time of their enrolment into the trial), in which the safety of prescribed drug therapy with glucocorticoids is being studied.

Nevertheless, if during the visit of the patient the investigator finds out the AE, occurred in this trial and on the background of the pharmaceutical product intake, it is necessary to ascertain whether there is or there is not a cause-effect relationship with the pharmaceutical product, collect and report information in accordance with regulatory requirements and timing for pharmacovigilance in the postmarketing period for spontaneous report.

For each adverse event it is necessary to record the following variables:

- a term for describing of the adverse event;
- date of occurrence and completion of the adverse event;
- severity of the adverse event;
- compliance of the adverse event with the criteria of seriousness;
- the investigator's assessment of the existence of a cause-effect relationship between the adverse event and the use of a pharmaceutical product (yes or not);
- Measures, taken in relation to the pharmaceutical product;
- The outcome.

It is extremely important, that all the staff, participating in the trial, are familiar with the contents of this section. The principal investigator is responsible for ensuring that all the staff, involved in the trial, are familiarized with the spontaneous report processing procedures (the term spontaneous report implies voluntary transfer by a health worker or the consumer to the Regulatory Authority, holder of the registration certificate), as well as with national regulatory requirements for pharmacovigilance in Russia.

### **Adverse events assessment**

All AE (both serious and non serious), spontaneously reported by patients or identified by the investigator, will be assessed for the presence or absence of causal relationship with pharmaceutical product and should be recorded and evaluated in accordance with the following definitions:

#### **Degree of severity**

To estimate the severity of AE concerning its intensity, the following three-level scale will be used:

- Mild: the presence of signs or symptoms that do not affect daily activities.
- Medium: the event is of sufficient intensity to affect daily activities.
- Severe: impossibility to work or perform daily activities (unacceptable event).

**Important!** The severity of events is not the equivalent of seriousness and is used to describe the intensity of an event (for example, a strong headache may not be of a serious clinical significance)

\*

\* See the seriousness criteria in the SAE definition or the item is defined by criteria in section 6.1.2.

### **Causality Assessment between the medicinal product and Adverse Event**

The investigator necessarily assesses the relationship between the use of the pharmaceutical product and the occurrence of each adverse event by answering "yes" or "no" to the question:

"Do you think that there is a reasonable probability that this event could be caused by the therapy used (for the drug in the glucocorticoid therapy)?».

## **6.3 Reporting on the adverse events**

### **6.3.1 Reporting on the adverse events spontaneous reports**

Monitoring of safety will be performed according to local pharmacovigilance requirements, applicable in standard medical practice on the territory of the Russian Federation.

If one of the investigators becomes aware of AE, which is estimated to have a causal relationship with the pharmaceutical product of AstraZeneca company, information on such AE should be collected and recorded in the primary documentation and in the form of an AE report (which is part of the eCRF).

All AR and serious adverse reaction (SAR), including fatal events, should be collected and the information should be transmitted in accordance with regulatory requirements and timing for pharmacovigilance in the postmarketing period for spontaneous report.

If the causal relationship is estimated as doubtful in the report (AE or SAE), that report should be included in the final report.

Information about all adverse events should be summarized and represented in the final clinical trial report.

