#### **4.4. Statistics analysis**

Primary and secondary statistical indicators will be presented using descriptive statistics methods. Qualitative variables will be presented in the form of incidence and percentage. The quantitative variables will be represented by numerical values, standard deviation indicators, minima and maxima, median and interquartile range. The frequency and severity of adverse events / reactions will be documented according to the Medical Dictionary of Regulatory Terminology, version 16.1. When analyzing the outcome of the disease among patients on therapy (drug), statistical analysis will be performed in a subgroup of newly identified patients. Evaluation of the outcome of SA can be determined by achieving a sufficient number of patients in a subgroup of newly identified patients and patients undergoing therapy (SA). The lack of comparison between groups of patients is due to the inaccuracy of these therapies in the history and treatment approaches.

In the course of the analysis, the standard statistical characteristics of morbidity, prevalence of the disease (SA) and their dependence on the basic demographic indicators (sex, age) will be assessed. The statistical analysis of the endpoints will be performed for patients with a diagnosis period of no more than 6 months from the date of inclusion in the register (a subgroup of newly identified patients) and also when the required amount of statistical data is collected within the register database.

The analysis will use standard methods of descriptive, frequency, logistic statistical analysis.

Hypotheses of the study. The main goal of the study is to obtain statistical estimates of the target epidemiological characteristics, formally asking questions about hypotheses of the study in this case is not applicable. After receiving the estimates, they are expected to be compared with similar ones, known in the foreign and domestic literature and official statistics.

Within the Registry, measures should be taken to collect data on the maximum number of patients within the claimed sample. In the absence of information within the fields of the individual registration card, the validating authority should separate information on the statuses "negative value", "no data", "not investigated".

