109	Management plan	Are there other factors affecting the symptoms of severe asthma?	- "interruptions" in state preferential drug provision; - Other
110	Management plan	Current patient management plan? (Select all that apply)	-Discharged for outpatient treatment of asthma -Current optimization of treatment - Prescription of biological therapy (specific drugs can be found in the list of active medicines) -Bronchial thermoplastics -Supporting oral glucocorticosteroids -Other (please specify)
111	Management plan	Recommendations on asthma therapy (drug (s), dose, regimen) at the current visit:	5 rows to enter - - - - -

112	Management plan	Supposed date of next visit	A reminder for the doctor and patient: - For two weeks, - for 1 week, - for 1 day.
113		What are the sources of preparations for baseline therapy in the patient?	- Self-acquisition; - State preferential drug provision: 1) Federal 2) Regional 4) In hospital drug provision 5) High technology medical care; 6) Territorial programs; 7) Other.
114	Tolerability	Do patients have AE due to the therapy for asthma?	-Indicate the suspected drug. -Fill in the AE registration form (at each visit and the form on AE should be attached to the company's drugs: 1) symbicort turbuhaler (budesonide + formoterol) 2) pulmicort suspension (budesonide)
115	Tolerability	Did the patient take part in randomized clinical trials to study monoclonal antibodies use?	- No - YES: Name of study?

---

---

[figure not shown]

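### The protocol contradicts itself on which adverse events enter the eCRF form, so the planned frequencies and the summary of all events have no settled numerator

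*Combined protocol and SAP*

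**What the plan says.** The combined protocol and SAP treats adverse events (AEs) in several places, and their scopes differ.

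- **Recording, broad.** Section 6.2 lists the variables to be recorded for each AE and sets no condition on the manufacturer. Its subsection on AE assessment covers every event, serious or not, whether the patient volunteers it or the investigator finds it. Section 6.3.1 also has all adverse reactions collected and passed on under post-marketing rules. Collection is passive: "active collection of safety data will not be performed".
- **eCRF form, narrow.** Section 6.3.1 sends to the eCRF AE report an event "which is estimated to have a causal relationship with the pharmaceutical product of AstraZeneca company". Appendix 9, item 114, starts widely, asking "Do patients have AE due to the therapy for asthma" and having the suspected drug entered. It then says that "the form on AE should be attached to the company's drugs", and names two products, both containing budesonide.
- **Causality, narrow.** The yes/no question must be answered for each AE, but it is worded "for the drug in the glucocorticoid therapy".
- **Output, broad.** Section 4.4: "The frequency and severity of adverse events / reactions will be documented". Section 6.3.1: "Information about all adverse events should be summarized and represented in the final clinical trial report". Section 4.5 takes all patients in the analysed population as the general denominator, with an exception for nested questions.
- **Purpose.** Section 2.0 names the safety of pharmacotherapy in the overall objective. Sections 2.1 and 2.2 list no safety item.

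**The concern.** A frequency needs a numerator and a denominator with the same scope. Here the planned output covers all AEs in all registry patients, while the two places that say when the eCRF form is completed refer to one company's products. A site that follows 6.3.1 and item 114 could report a reaction to another company's biologic to the regulator and never complete the registry form. A site that follows 6.2 would complete it. The pooled table would then mix two rules, and nobody could tell afterwards which site had used which.

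The causality item adds to this. For a biologic, LAMA, leukotriene antagonist, theophylline or macrolide, all of which the Appendix records, the question as worded does not ask about the drug under suspicion. A yes or no in that field would have no clear meaning.

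**Working it through.** The plan states no AE rate, precision or product share, so there is no figure to reproduce. The check is a comparison of the texts, followed by an illustration on assumed inputs.

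**Step 1. Follow four kinds of event through the text.**

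1. *Reaction attributed to one of the two named products.* Sections 6.2 and 6.3.1 and item 114 all lead to the form, and the causality question fits. No conflict.
2. *Reaction attributed to another company's biologic.* Section 6.2 says record it. The trigger in 6.3.1 is not met and the product is not named in item 114. The causality question does not fit. The final report is still meant to include it.
3. *Reaction attributed to an oral corticosteroid of another company.* The form is uncertain, as in case 2, but rows 85 and 86 collect OCS adverse effects whoever makes the drug. The variable list shows no dates, severity, seriousness or outcome of the effect in those rows, so capture is partial.
4. *Event on a sponsor product judged unrelated.* Section 6.2 says record it. The trigger in 6.3.1 needs a positive causal judgement. Yet 6.3.1 wants reports of doubtful causality and all AEs in the final report.

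The texts agree only in case 1. The two narrow texts are also not identical: 6.3.1 covers any product of the sponsor, while item 114 names two.

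**Step 2. Direction of the effect if the narrow texts govern.** Let r be the share of patients with a drug-related AE that comes to the investigator's notice, and s the share of those AEs attributed to a sponsor product. With one attributed event per affected patient and all patients as denominator,

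reported frequency = r × s, and share lost = 1 − s.

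Neither r nor s is in the documents. N = 7,000 is the target maximum in section 3.1. Cells give the reported percentage and the number of patients.

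| r (patients) | s = 0.2 | s = 0.5 | s = 0.8 | s = 1 (6.2 governs) |
|---|---|---|---|---|
| 5% (350) | 1.0% (70) | 2.5% (175) | 4.0% (280) | 5% (350) |
| 10% (700) | 2.0% (140) | 5.0% (350) | 8.0% (560) | 10% (700) |
| 20% (1,400) | 4.0% (280) | 10.0% (700) | 16.0% (1,120) | 20% (1,400) |

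For example, 0.10 × 0.2 = 0.02, and 0.02 × 7,000 = 140. The loss is 80%, 50% and 20% at s = 0.2, 0.5 and 0.8, and nil at s = 1.

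**Step 3. Denominator.** The table uses the general rule in 4.5. If AE detail counts as nested under item 114, the exception in 4.5 would instead use patients with a positive answer there. Section 4.4 does not say which applies.

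**The case against.** The strongest reply is that neither narrow text says only. Section 6.3.1 tells sites to put sponsor-related AEs on the form and does not forbid others. The same section has all adverse reactions collected, and 6.2 asks for each AE to be recorded. Item 114 is garbled, and could mean that the form is completed at every visit with something further for company drugs. No text describes eCRF logic that locks the form to certain products. On that reading s = 1 and nothing is lost.

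This reply stands as far as it goes: product-selective capture is possible, not established. It does not remove the contradiction. Section 6.2 does not say where in the registry the record is made, and the only places that say when the eCRF form is completed are company-specific. Nor does the reply touch the causality wording.

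A reader might go further in the other direction. The documents do not support these inferences:

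- *The AE summary is bound to be product-selective, with every recorded reaction on a sponsor drug.* This ignores the broad recording text, the OCS rows, and item 114's request for the suspected drug under any asthma therapy.
- *Signals on newer drugs would go unseen.* Section 6.3.2 still sends reactions to the federal regulator and to the holder of the registration certificate, whichever company that is.
- *Comparisons between drugs would be distorted.* No AE table by drug is planned, and 4.4 disclaims comparison between patient groups.

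**Conclusion.** The contradiction is real and should be corrected, because sections 4.4 and 6.3.1 promise results whose content the protocol does not fix. The primary objective, the distribution of exacerbation frequency at enrolment, is not affected.

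The bias is conditional. If 6.3.1 and item 114 govern, form-level AE data on biologics and other companies' drugs are incomplete, and with an all-patient denominator the reported frequency is too low by the factor s. If 6.2 governs, this loss does not arise. The true size cannot be derived; the table above only shows how it depends on r and s, and it assumes one attributed event per patient although the Appendix records concurrent therapies.

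Two limits remain under either reading. Collection is passive, so even a product-neutral form yields reporting frequencies and not incidence. And safety stands only in the overall objective, so the point concerns a descriptive summary and not a listed endpoint.

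**What to change.** 1. Reconcile section 6.2 (including its AE and causality assessment subsections), section 6.3.1 and item 114, so that the eCRF AE form is completed for whatever drug is entered as suspected in item 114.
2. Word the causality question for that drug.
3. Leave the routing to the regulator and the registration holder unchanged.
4. In 4.4, state that the results are reporting frequencies under passive collection and not incidence. Name the denominator, including whether the nested-question rule of 4.5 applies.

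The cost is a few extra AE forms per site and a small eCRF text change.

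If this is not accepted, limit the AE summary in 4.4 and 6.3.1, and the safety wording in 2.0, to a listing of the events that the form actually captures, without population frequencies. Section 6.2 must then be aligned, or the contradiction remains. This version costs wording only, but it gives up any registry-wide statement on AE frequency.

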### **6.3.2 Recording of spontaneous the adverse events**

When recording adverse events, identified in the trial, it is necessary to be guided by the following principles: the investigator should report on adverse events by the pharmacovigilance procedures according to local regulatory requirements.

Method of presenting information on AR/SNR, obtained in the spontaneous reporting:

1. In writing to the Federal Service for Surveillance in Healthcare by contacting: Russian Federation, [name] At the same time, it is necessary to use a special form located at:

<http://www.roszdravnadzor.ru/i/upload/files/1308641445.19876-26263.doc>

2. To the relevant pharmaceutical company, i.e. company, in whose name a registration certificate of the pharmaceutical product has been issued, according to local regulatory requirements.

## **7. Publication Plan**

Dissemination plan for research results and communications on the results obtained. The results of the study, annual reports will be compiled.

A number of publications are planned on the basis of the statistical analysis of the research data, the authors' team, the internal editing and review procedures will be decided within the working group on the publication policy. The timing of publications and their content will be regulated by the Core Steering Committee, the curators of the study.

Intellectual property rights belong to the executors of the project:

- 1) Interregional Public Organization "Russian Respiratory Society".
- 2) Russian Association of Allergology and Clinical Immunology.

## 9. APPENDIX: Main variables

	Category	Variable's Fields Names	Response options (if applicable)
1	Inclusion Criteria	Is the patient suffering from uncontrolled asthma and taking medium-to-high doses of ICS?  Please check one of the following:  1. At the stage 5 GINA  2. (a) Uncontrolled in Stage 4: There are symptoms of severe asthma  2. (b) Uncontrolled in stage 4: there are exacerbations requiring OCS	No/Yes
2	Inclusion Criteria	The patient meets the criteria for the inclusion in RSAR	No/Yes
3	Detailed description of the patient	Visit date	DD / MM / YYYY
4	Detailed description of the patient	Date of Birth  Age at the moment of examination	DD / MM / YYYY  Full age (calculated automatically)
5	Detailed description of the patient	Gender	Male/female
6	Detailed description of the patient	Race	Caucasian / Southeast Asian / Northeast Asian / African / Mixed / Other
7	Detailed description of	IIIT	Decimal number (calculated automatically)

	the patient		
8	Detailed description of the patient	BMI	Decimal number (calculated automatically)
9	Detailed description of the patient	Height	Decimal number
10	Detailed description of the patient	Weight	Decimal number
11	Detailed description of the patient	Was the bronchial thermoplastics given to the patient?	No/Yes
12	Occupation	What is the current patient's occupation?	Free text entry
	Occupation	Occupational risks	- at the moment; - in anamnesis.
13	Anamnesis	What is current smoking status of a patient?	Never smoked / Former smoker / Currently smokers
14	Anamnesis	-Number of cigarettes smoked daily? (if marked "ex-smoker", "currently smokes")	Number
15	Anamnesis	-Years of smoking? (please indicate the period of time during which the patient smoked continuously)	Number
16	Anamnesis	-Pack-Years	Number (calculated automatically)
17	Anamnesis	-Years, passed after you quit smoking?  (please specify the time period from which the patient stopped smoking)	Number

18	Anamnesis	At what age did the symptoms of asthma start to appear in the patient?  Full years or months, if <1 year	Number
19	Anamnesis	Number of exacerbations requiring treatment with systemic glucocorticosteroids in the last 12 months?	Number
20	Anamnesis	The total number of episodes of invasive pulmonary ventilation?	Number
21	Anamnesis	Total number of ambulance calls due to asthma in the last 12 months?	Number
22	Anamnesis	Total number of hospitalizations due to asthma in the last 12 months?	Number
23	Anamnesis	Indicate the number disability episodes in the last 12 months (for BA).	Number
24	Significant concomitant diseases	Atopic dermatitis  Atopic disease: yes, if atopic dermatitis is noted	Never / in the past / currently
25	Significant concomitant diseases	Allergic rhinitis  Atopic disease: yes, if allergic rhinitis is noted	Never / in the past / currently
26	Significant concomitant diseases	Non-allergic rhinitis	Never / in the past / currently
27	Significant concomitant diseases	Chronic rhinosinusitis with polyps	Never / in the past / currently
28	Significant concomitant diseases	Chronic rhinosinusitis without polyps	Never / in the past / currently

29	Treatment of significant concomitant diseases	Atopic dermatitis Allergic rhinitis Non-allergic rhinitis Chronic rhinosinusitis with polyps Chronic rhinosinusitis without polyps	Indicate treatment of significant concomitant diseases
30	Significant concomitant diseases	Indicate concomitant diseases in the patient	obesity, - Type 2 diabetes, - Arterial hypertension, - IHD, - COPD, - CHF, - CRF; other.
31	Treatment of significant concomitant diseases	obesity, - Type 2 diabetes, - AH, - IHD, - COPD, - CHF, - CRF; other.	Indicate treatment of significant concomitant diseases
32	Blood/ sputum	What was the largest number of eosinophils of blood (over the last year)?	Decimal number
33	Blood/ sputum	- Date of the maximal number of eosinophils of blood (for the last year)	DD / MM / YYYY

34	Blood/ sputum	-Was the greatest number of eosinophils of blood recorded during exacerbation?	No/Yes
35	Blood/ sputum	What was the maximal number of eosinophils of the blood? (for the last year and beyond the exacerbation)	Decimal number
36	Blood/ sputum	Date of the maximal number of eosinophils of blood (for the last year and without exacerbation)	DD / MM / YYYY
37	Blood/ sputum	Current (last) value of eosinophils	Decimal number
38	Blood/ sputum	-Last date of eosinophils measurement	DD / MM / YYYY
39	Blood/ sputum	What was the maximal number of eosinophils in sputum (over the last year)? (in percentages)	Decimal number
40	Blood/ sputum	- Date of the maximal number of eosinophils of blood (for the last year)	DD / MM / YYYY
41	Blood/ sputum	What is the current IgE value (last)?	Decimal number
42	Blood/ sputum	- Date of current IgE measurement (latest)	DD / MM / YYYY
43	Blood/ sputum	Was the patient's periostin level measured?	- Yes; - No;
45	Diagnostics	Was chest radiography performed?	Normal/ Abnormal/Was not performed
46	Diagnostics	Was chest computer tomography performed?	Normal/ Abnormal/Was not performed
47	Diagnostics	-Date of chest computer tomography	DD / MM / YYYY
48	Diagnostics	Was densitometry done?	No/Yes
49	Diagnostics	Date of densitometry	DD / MM / YYYY

50	Lung function	FEV1 before broncholytic	Decimal number
51	Lung function	FEV1 after broncholytic	Decimal number
52	Lung function	Functional Vital capacity before broncholytic	Decimal number
53	Lung function	Functional Vital capacity after broncholytic	Decimal number
54	Lung function	Prognosed FEV1	Decimal number (calculated automatically)
55	Lung function	FEV1 before broncholytics (% of prognosed)	Decimal number (calculated automatically)
56	Lung function	FEV1 after broncholytics (% of prognosed)	Decimal number (calculated automatically)
57	Lung function	Prognosed FVC	Decimal number (calculated automatically)
58	Lung function	FVC before broncholytics (% of prognosed)	Decimal number (calculated automatically)
59	Lung function	FVC after broncholytics (% of prognosed)	Decimal number (calculated automatically)
60	Lung function	The ratio of FEV1 / FVC before bronchodilator	Decimal number (calculated automatically)
61	Lung function	The ratio of FEV1 / FVC after bronchodilator	Decimal number (calculated automatically)
62	Lung function	Spirometry	DD / MM / YYYY
63	Lung function	Was the test for methacholine PC20 / histamine/exercise performed?	No/Yes
64	Lung function	-Date of PC20 test	DD / MM / YYYY
65	Lung function	- PC20 result	Decimal number (calculated automatically)
66	Lung function	An exhaled nitric oxide test was performed?	No/Yes

67	Lung function	- Date of analysis for expired nitric oxide	DD / MM / YYYY
68	Lung function	- Results of the analysis for expired nitric oxide	Decimal number (calculated automatically)
69	Allergic tests (ALL)	Was the environmental allergens test performed?	Determination of specific IgE in blood/Scarification test/Was not done
70	Allergic tests (determination of specific IgE in blood)	- Date of determination of specific IgE in blood	DD / MM / YYYY
71	Allergic tests (determination of specific IgE in blood)	- Was specific IgE in blood positive for year-round allergens?	No/Yes
72	Allergic tests (determination of specific IgE in blood)	+ Indicate the year-round allergens to which specific IgE in blood was positive (select all applicable)	Dust mite (eg D. Pteronyssinus) / cat's hair / mixture of molds / dog hair / aspergillus / other (please specify)
73	Allergic tests (determination of specific IgE in blood)	- Was specific IgE in blood positive for seasonal allergens?	No/Yes
74	Allergic tests (determination of specific IgE in blood)	+ Indicate the seasonal allergens to which specific IgE in blood was positive (select all applicable)	Trees pollen Weeds pollen Grasses pollen
75	Allergic tests (Scarification test (ST))	-ST date	DD / MM / YYYY
76	Allergic tests (Scarification test (ST))	- Was the ST positive for year-round allergens?	No/Yes

77	Allergic tests (Scarification test (ST))	Indicate year-round allergens (for ST) (select all applicable)	Dust mite (eg D. Pteronyssinus) / cat's hair / mixture of molds / dog hair / aspergillus / other (please specify)
78	Allergic tests (Scarification test (ST))	- Was the ST positive for seasonal allergens?	No/Yes
79	Allergic tests (Scarification test (ST))	+ Indicate the seasonal allergens to which the ST was positive (select all applicable)	Trees pollen Weeds pollen Grasses pollen
80	Asthma symptom control	Do patients experience symptoms during the day? (more than twice a week)	No/Yes
81	Asthma symptom control	Does the patient have any limitation of physical activity due to asthma? For what period of time?	No/Yes
82	Asthma symptom control	Does patient awake For what period of time?	No/Yes
83	Asthma symptom control	Does patient need to use asthma symptom relief drugs more than 2 a week?	No/Yes
84	Asthma symptom control	Is the patient's lung function (PEF or FEV1) < 80% of prognosed or best per sonal result (if known)?	No/Yes
85	Drugs to manage asthma	Does patient use currently oral GCS?	No/Yes – Dose - Duration of use - Registered adverse

			effects of OCS
86	Drugs to manage asthma	Did patient use OCS earlier?	No/Yes – Dose - Duration of use - Registered adverse effects of OCS
87	Drugs to manage asthma	-Date of OCS use start	DD / MM / YYYY
88	Drugs to manage asthma	Does patient use currently combined therapy (ICS+LABA)? (please, select from the list)	No budesonide + formoterol fluticasone furoate + vilanterol fluticasone propionate + salmeterol beclomethasone + formoterol other
89	Drugs to manage asthma	Does the patient currently take ICS + LABA as a fixed or free combination?	- Fixed combination - Free combination
90	Drugs to manage asthma	- Date of onset of combined ICS+LABA therapy	DD / MM / YYYY

91	Drugs to manage asthma	Is the patient currently taking ICS (only)? (please select from the list)	No triamcinolone acetonide mometasone furoate fluticasone propionate fluticasone furoate ciclesonide flunysonide budesonide beclomethasone other
92	Drugs to manage asthma	- Date of start / end of ICS intake	DD / MM / YYYY
93	Drugs to manage asthma	Is the patient currently taking LABA (only)? (please select from the list)	No formoterol salmeterol indacaterol olodaterol other
94	Drugs to manage asthma	- Date of start / end of LABA intake	DD / MM / YYYY
95	Drugs to manage asthma	Is the patient currently taking LAMA (only)? (please select from the list)	No aclidinium tiotropium umeclidinium glycopyrronium

			other
96	Drugs to manage asthma	- Date of start / end of LAMA intake	DD / MM / YYYY
97	Inhalation technique assessment.	Appropriate Inappropriate (if so, the next question) Crucial mistakes Present Absent	
98	Drugs to manage asthma	Is the patient currently taking theophylline? (please select from the list)	No theophylline aminophylline other
99	Drugs to manage asthma	- Date of start / end of theophylline intake	DD / MM / YYYY
100	Drugs to manage asthma	Is the patient currently receiving a leukotriene receptor antagonist (LTRA)? (please select from the list)	No zafirlukast montelukast other
101	Drugs to manage asthma	- Date of start / end of LTRA intake	DD / MM / YYYY
102	Drugs to manage	Is the patient currently receiving treatment targeted on	No/Yes

	asthma	immunoglobulin E (Anti-IgE)? (omalizumab is prescribed)	
103	Drugs to manage asthma	Date of start / end of Anti-IgE intake?	DD / MM / YYYY
104	Drugs to manage asthma	Is the patient currently receiving treatment targeted on IL-5 (Anti-IL-5)? (please select from the list)	No reslisumab mepolizumab benalizumab dupilumab (?) tezepelumab (?) other (new biotechnological preparations will be added after approval and start of use in Russia)
105	Drugs to manage asthma	Date of start / end of Anti-IL5 intake?	DD / MM / YYYY
106	Drugs to manage asthma	Does the patient currently receive antibiotic treatment with the macrolide group? (please select from the list)	No azithromycin clarithromycin erythromycin roxithromycin fidaxomycin telithromycin other
107	Drugs to manage	Date of start / end of macrolide	DD / MM / YYYY

	asthma	intake?	
108	Compliance	Is there a non-compliance with the treatment regimen?	No Yes: - dosage; - frequency of reception; - absence of all prescribed medications; - other
109	Management plan	Are there other factors affecting the symptoms of severe asthma?	- "interruptions" in state preferential drug provision; - Other
110	Management plan	Current patient management plan? (Select all that apply)	-Discharged for outpatient treatment of asthma -Current optimization of treatment - Prescription of biological therapy (specific drugs can be found in the list of active medicines) -Bronchial thermoplastics -Supporting oral glucocorticosteroids -Other (please specify)
111	Management plan	Recommendations on asthma therapy (drug (s), dose, regimen) at the current visit:	5 rows to enter - - - - -

112	Management plan	Supposed date of next visit	A reminder for the doctor and patient: - For two weeks, - for 1 week, - for 1 day.
113		What are the sources of preparations for baseline therapy in the patient?	- Self-acquisition; - State preferential drug provision: 1) Federal 2) Regional 4) In hospital drug provision 5) High technology medical care; 6) Territorial programs; 7) Other.
114	Tolerability	Do patients have AE due to the therapy for asthma?	-Indicate the suspected drug. -Fill in the AE registration form (at each visit and the form on AE should be attached to the company's drugs: 1) symbicort turbuhaler (budesonide + formoterol) 2) pulmicort suspension (budesonide)
115	Tolerability	Did the patient take part in randomized clinical trials to study monoclonal antibodies use?	- No - YES: Name of study?

---

---

[figure not shown]
